### **10.1.2 Analysis of Continuous Variables**

For continuous variables, the model based mean and standard error will be provided. The Baseline and visit means will also be presented for each treatment group. The treatment groups will be compared using the analysis of covariance (ANCOVA) model with treatment group and stratification factors as fixed effects, and the corresponding baseline value as covariates. Point estimates and 95% CIs of mean change from baseline within treatment groups, and between each upadacitinib treatment group and placebo will be provided.

### **10.1.3 Analysis of Time to Event Variables**

For the time to event endpoints, the time to event will be calculated as:

- Time to first event (as observed) = [date of first event in Period 1] – [date of first study drug in Period 1] + 1;
- If a subject never attains an event in Period 1, then that subject's time to first achievement will be censored at the last visit where the variable was measured in Period 1.

Time to EASI 50/75/90 response and IGA "0" or "1" response will be evaluated for Period 1. Time to loss of EASI 50 response among those who were re-randomized as EASI 75 responders at Week 16 will be evaluated for Period 2.

Time to event variables will be analyzed by stratified log-rank test adjusting for stratification factors.

#### **10.1.4 Analysis of Dose Response**

The dose-response relationship among the 3 upadacitinib dose groups and the placebo group will be characterized for the primary efficacy endpoint percent change from Baseline in EASI score at Week 16 and two secondary endpoints of EASI 75 and IGA 0/1 at Week 16 using the Multiple Comparison Procedure – Modeling (MCP-Mod) method. The response based on the LOCF imputation will be used, and ADDPLAN DF software will be used to perform the MCP-Mod analyses.

A set of six pre-specified standardized candidate dose-response models, as described in [Table 13](#) will be utilized to examine the dose-response relationship. For each endpoint separately, a statistically significant dose response relationship will be declared if at least one model is identified by the MCP-Mod method to be statistically significant at the level  $\alpha = 0.05$  one-sided. The fitted dose-response curves will be presented graphically for all statistically significant models along with confidence bands. The MED will be identified for each statistically significant model based on the pre-specified clinical meaningful target of a 20% target difference from placebo. The weighted MED across all significant models will be calculated, with weights being the inverse of model AIC.

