8.1.5 Statistical Analyses of Efficacy

The efficacy analysis will be conducted in the ITT Population, and Per-protocol Population if defined, in each Period. Visit windows and the data handling conventions for summarizing efficacy results will be defined in the Statistical Analysis Plan. Missing data will be imputed using the following methods for the efficacy analyses in the ITT Populations:

- Non-Responder Imputation (NRI): the NRI analysis will categorize any subject who has missing value at a specific visit as non-responder for that visit. In NRI analysis, subjects who prematurely discontinue study drug will be considered non-responders on or after discontinuation date. NRI will be the primary approach for binary endpoints.
- Last Observation Carried Forward (LOCF): The LOCF analyses will use the completed evaluation from the previous visit to impute missing data at later visits. Baseline value will not be carried forward. LOCF will be the primary approach in the analysis of continuous variable, and the secondary approach in the analysis of categorical variables.

- As-observed (OC): The OC analysis will not impute values for missing evaluations, and thus a subject who did not have an evaluation on a scheduled visit will be excluded from the as observed analysis for that visit. As-observed analysis will be the secondary approach in the analysis of continuous variables.
- Multiple Imputation (MI): The MI analysis imputes missing data multiple times under appropriate random variation and thus generates multiple imputed "pseudo-complete" datasets. Results will be aggregated across the multiple imputed datasets, overcoming drawbacks of the single imputation methods. MI will be performed for the primary efficacy variable and the proportion of subjects achieving IGA of "clear" or "almost clear" and EASI 75 at Week 16.

Efficacy parameters for the subjects who are rescued with 30 mg ABT-494 or topical corticosteroids in Period 2, and subjects who discontinued study drug due to EASI score worsening during Period 1 will be imputed from the point of rescue using non-responder imputation for categorical variables or LOCF for the continuous variables.

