### 10.1.5 Missing Data Imputation

Missing data will be imputed using the following methods for the efficacy analyses:

- Non-Responder Imputation (NRI): the NRI analysis will categorize any subject who does not have evaluation during a specific visit window as a non-responder for that visit. The exception is when the subject is a responder both before and after a specific visit window, in which case the subject will be categorized as a responder for the visit. Only observations within the same analysis period will be used. The NRI will be the primary approach in the analyses of categorical variables.

- Last Observation Carried Forward (LOCF): The LOCF analyses will carry forward the most recent previous non-missing value (last completed non-missing value, for composite endpoint) to impute missing data at later visits in the same period. Baseline efficacy evaluations will not be carried forward. LOCF will be the primary approach in the analyses of continuous variables, and the secondary approach in the analysis of categorical variables.
- As-Observed Cases (OC): The as-observed analysis will not impute values for missing evaluations, and thus a subject who does not have an evaluation on a scheduled visit will be excluded from the as-observed analysis for that visit. As-observed analysis will be the secondary approach in the analysis of continuous variables.
- Multiple Imputation (MI): The MI approach will be used for sensitivity analyses on the Week 16 endpoints of EASI percent change from Baseline, EASI 75, and the Investigator Global Assessment (IGA) response of 0 (clear) or 1 (almost clear). If MI is not applicable due to the nature of the data (e.g., MCMC algorithm does not converge), logistic regression or mixed effect model repeat measurement (MMRM) methods will be applied as the sensitivity approach, whichever applicable.

The Multiple Imputation analysis will be carried out in three steps.

- Imputation of missing data. The imputation will be generated for each efficacy endpoint measurement. The variables to be included in the imputation model are: Baseline EASI (or IGA), treatment group, and measurements at each visit up to the end of the analysis period. For each endpoint, 20 'complete' datasets will be generated using SAS PROC MI. The imputed post-baseline measurements will be rounded to the same precision as the observed data before the determination of responder status (e.g., EASI 75 and EASI percentage change from Baseline).

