  - Analysis of imputed data sets. Using the corresponding statistical methods for the categorical and continuous endpoints, the imputed endpoints from Step 2 will be analyzed using each of the 20 datasets.
-

- Synthesis of imputation and analysis results. SAS PROC MIANALYZE will be used to generate the final inferences of the risk difference between treatment groups.

Of note, subjects who take rescue upadacitinib 30 mg or take rescue topical treatment in Period 2 will have their efficacy assessments taken from the date after the first dose of rescue excluded from the analyses, as the result, the subjects will be considered as non-responders in the NRI approach, and have their last observations on or prior to the date of rescue carried forward, and be removed from the OC approach.

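### The dose-response test, curve and MED for EASI 75 and IGA 0/1 are specified only on LOCF data, although NRI is primary for binary endpoints; the primary MCP-Mod names no covariates

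*SAP*

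**What the plan says.** **Dose-response.** SAP 10.1.4 applies MCP-Mod to percent change in EASI and to EASI 75 and IGA 0/1, all at Week 16. One imputation sentence covers all three: "The response based on the LOCF imputation will be used, and ADDPLAN DF software will be used to perform the MCP-Mod analyses". The same section takes the MED from each significant model against a "pre-specified clinical meaningful target of a 20% target difference from placebo". SAP 10.5 mentions the two binary MCP-Mod analyses again, under exploratory variables, and names no imputation.

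**Imputation hierarchy.** Protocol 8.1.5: "NRI will be the primary approach for binary endpoints". SAP 10.1.5 agrees: "The NRI will be the primary approach in the analyses of categorical variables". On LOCF it says: "LOCF will be the primary approach in the analyses of continuous variables, and the secondary approach in the analysis of categorical variables". Multiple imputation is a sensitivity method: "The MI approach will be used for sensitivity analyses on the Week 16 endpoints of EASI percent change from Baseline, EASI 75", and also IGA 0/1. Its last step is described as a pooled treatment comparison: "SAS PROC MIANALYZE will be used to generate the final inferences of the risk difference between treatment groups". Nothing links it to MCP-Mod or the MED.

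**NRI and stopping study drug.** Protocol 8.1.5: "In NRI analysis, subjects who prematurely discontinue study drug will be considered non-responders on or after discontinuation date". The NRI paragraph of SAP 10.1.5 does not mention stopping study drug. SAP 4.2 keeps such subjects in scheduled follow-up unless they withdraw consent.

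**Covariates.** SAP 10.1.4 and 10.3 name none for the primary MCP-Mod. SAP 10.1.2 specifies an ANCOVA with the stratification factors (region, in Period 1) and the baseline value for continuous variables, without tying it to MCP-Mod. Protocol 8.1.5.1 plans an additional model with baseline terms for the primary endpoint and does not name the terms.

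**The concern.** For percent change in EASI, LOCF is the declared primary method, so the MCP-Mod follows the hierarchy. For EASI 75 and IGA 0/1 it does not. The report would show NRI response rates and CMH comparisons beside a curve and MED fitted to different rates, and no planned analysis would show whether the difference matters. Estimating target doses such as the MED is one of the stated aims of the sample size section, so this output may be used when doses are chosen.

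The covariate gap matters less. With none named, the MCP-Mod and the ANCOVA of the same endpoint can give different dose-placebo differences, and the choice of adjustment stays open until the data are seen.

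The NRI gap is separate. A subject who stops study drug, is followed and meets EASI 75 at Week 16 is a non-responder under the protocol but could be counted as a responder under the SAP's wording.

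**Working it through.** **1. The plan's own figures.** Inputs (SAP 4.3, Protocol 8.2): mean improvement 35, 45, 60 and 70 for placebo, 7.5, 15 and 30 mg; SD 40; 40 per group. SE of a pairwise difference = 40·√(2/40) = 8.94. With a two-sided 5% t test on 78 df, a difference of 25 gives 78.8% (stated 78%) and 35 gives 97.2% (stated 97%). MCP-Mod with the protocol's five models, one-sided 5%, gives 99.3% average power for a rise from 35 to 70; the SAP's six models give 99.2% (stated 99%). All were obtained without covariates, so nothing below disturbs them.

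**2. Implied EASI 75 rates.** Assuming normality, rate = P(Z ≥ (75 − mean)/40) = 15.9, 22.7, 35.4 and 45.0%. The 15 mg minus placebo difference is 19.5 points, next to a 20-point target if 20% means percentage points (an assumption).

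**3. NRI against LOCF.** Let d be the share missing at Week 16 and q the share of those carried forward as responders. NRI rate = p(1 − d); LOCF rate = p(1 − d) + d·q. The gap in each arm is d·q. Both d and q are assumptions.

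**4. MED.** Lowest dose up to 30 mg at which an unweighted least-squares fit to the four rates exceeds placebo by 0.20. For the linear model, slope = Σ(dose − 13.125)·rate / 492.19 and MED = 0.20/slope. Scenario B under NRI: 4.414/492.19 = 0.00897, MED 22.3 mg; under LOCF: 4.733/492.19 = 0.00962, MED 20.8 mg. Emax uses ED50 ≤ 45 mg. Arms are in the order placebo, 7.5, 15, 30 mg.

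| Scenario | LOCF minus NRI, active vs placebo (points) | Linear MED, NRI → LOCF (mg) | Emax MED, NRI → LOCF (mg) |
|---|---|---|---|
| A: q = 0, or equal d and q in all arms | 0 | no shift | no shift |
| B: d = 10%; q = 10/20/30/30% | +1/+2/+2 | 22.3 → 20.8 | 18.6 → 16.8 |
| C: d = 20%; q = 10/20/30/40% | +2/+4/+6 | 25.1 → 20.1 | 22.1 → 16.1 |
| D: d = 20% placebo, 5% active; q = 20% | −3 in each | 19.8 → 21.5 | 15.5 → 17.7 |

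Across the six Table 13 models the MED falls 1.3–2.4 mg in B, falls 4.1–6.0 mg in C and rises 1.5–3.6 mg in D. Without the ED50 cap, Emax gives 19.5 → 17.2, 22.8 → 16.8 and 15.5 → 19.0 mg. Heavier assumptions give more. With 30% missing in every arm and q equal to the arm's own rate, the linear MED is 28.7 mg on NRI and 20.1 mg on LOCF. With 10/15/20/30% missing it is 34.0 mg (outside the dose range) against 20.1 mg. With placebo-heavy 30/20/15/10% it is 20.0 against 20.1 mg.

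**5. Sampling error.** 95% half-width for 15 mg minus placebo = 1.96·√(0.354·0.646/40 + 0.159·0.841/40) = 18.7 points. In 10,000 simulated complete-data trials the Emax MED had a 10th–90th percentile range of 7.9–22.2 mg among trials that had one; 12.9% had none within 30 mg. Within the same simulated trial, an Emax MED within 30 mg existed under one rule but not the other in 0% (A with q = 0), 7.7% (B), 19.6% (C) and 9.2% (D).

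**6. Covariates.** Half-width for 30 mg minus placebo = t(156)·40·√(1 − R²)·√(2/40), where R is the assumed correlation of the covariates with outcome: 17.7 points at R = 0, 17.3 at 0.2 and 16.2 at 0.4.

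**7. NRI rule.** If a share s stop drug but are followed, and a share r of those respond at Week 16, the two readings differ by s·r: from 0.05 × 0.10 = 0.5 points to 0.10 × 0.30 = 3 points per arm (s and r assumed).

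**The case against.** SAP 10.1.4 is explicit and can be programmed, and SAP 10.1.5 allows LOCF as a secondary method for categorical variables. A reader might infer that the SAP contradicts itself; it does not. The binary MCP-Mod is supportive, is listed again under exploratory variables, and SAP 10.6 makes no multiplicity adjustment. This stands and limits the weight of the point. What it leaves open is why the second-ranked method is the only one used for these curves and MEDs.

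The illustration is also open to attack, and fairly. Normal(70, 40) puts 22.7% of the 30 mg arm above 100% improvement, which EASI cannot show. The SAP gives no fitting scale for proportions: a logit-scale Emax in scenario D gives 15.9 → 19.5 mg. Five of the six capped Emax fits behind B to D sit on the 45 mg bound. Neither the SAP's inverse-AIC weighted MED nor any IGA 0/1 figure was computed. The numbers show possible sensitivity, not an expected bias.

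A reader might infer that the SAP dropped the protocol's rule on stopping study drug. The SAP presents itself as elaborating the protocol, so its silence can equally mean that the rule still applies. It needs clarifying; a change is not shown. A reader might also say that the protocol confines MCP-Mod to the primary endpoint. Protocol 8.1.5.1 names only that endpoint but excludes no other, and the SAP states the extension openly. Its absence from SAP 12.1 is housekeeping.

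On covariates, the powers reproduce without any, so the omission is not an error. The documents do not say whether the named software accepts adjusted means.

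**Conclusion.** The point holds as one of specification. The dose-response test, curve and MED for EASI 75 and IGA 0/1 rest on the method ranked second for such endpoints, without a reason or an NRI counterpart. In the moderate scenarios the MED shifts by 0 to 6.0 mg, in either direction. That is small beside sampling error, though it can decide whether a MED is reported within the dose range. Heavier assumed dropout can widen the gap; nothing in the documents supports a particular rate. All of this assumes 20 percentage points, normality and invented dropout.

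The tempting stronger reading is that LOCF flatters the drug or lowers the MED. The documents do not support it: the sign depends on missing data by arm, and scenario D goes the other way. The primary endpoint's LOCF rule and the 97%, 78% and 99% powers stand. The choice of LOCF for MCP-Mod does not touch the NRI-based CMH comparisons. The unresolved rule on stopping study drug could, because it would change the NRI rates those tests use.

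The missing covariates concern precision only, and the gain may be small.

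**What to change.** - **SAP 10.1.4:** state that MCP-Mod uses the LOCF response for percent change in EASI and the NRI response for EASI 75 and IGA 0/1, with LOCF (and MI, if wanted) as sensitivity for the two binary endpoints. Say whether the 20% MED target means percentage points. Refer to this from 10.5. If LOCF is kept as the main method for the binary endpoints, give the reason in 12.1.
- **SAP 10.1.4 and 10.3:** name the covariates for the primary MCP-Mod. Run it on the dose means and their covariance matrix from an ANCOVA with dose as a factor, region and baseline EASI.
- **SAP 10.1.5:** state whether subjects who stop study drug count as non-responders under NRI from that date, so that it agrees with Protocol 8.1.5; otherwise list the change in 12.1.
- **SAP 12.1:** for completeness, list the extension of MCP-Mod to the two binary endpoints.

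The cost is SAP wording and modest programming, with no new data. The one practical check is whether the named software accepts adjusted means and a covariance matrix; if not, other software is needed for that step. These choices should be fixed before the Period 1 unblinding.

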**Table 13. Candidate Models**

Model	$f(d, \theta)$ $d = \text{dose},$ $\theta = \text{Model Parameters}$	$f^0(d, \theta)$ Standardized Model	Initial Value(s) for Parameter(s)
Linear	$E_0 + \delta d$	$d$	NA
Exponential	$E_0 + E_1 \left[ \exp\left(\frac{d}{\delta}\right) - 1 \right]$	$\exp\left(\frac{d}{\delta}\right) - 1$	$\delta = 10$
Logistic	$E_0 + \frac{E_{max}}{1 + \exp\left(\frac{ED_{50} - d}{\delta}\right)}$	$\frac{1}{1 + \exp\left(\frac{ED_{50} - d}{\delta}\right)}$	$ED_{50} = 15, \delta = 5$
EMax	$E_0 + \frac{E_{max}d}{ED_{50} + d}$	$\frac{d}{ED_{50} + d}$	$ED_{50} = 15$
sigEMax	$E_0 + \frac{E_{max}d^h}{ED_{50}^h + d^h}$	$\frac{d^h}{ED_{50}^h + d^h}$	$ED_{50} = 15, h = 2.5$
Quadratic	$E_0 + \beta_1 d + \beta_2 d^2$	$d + \frac{\beta_2}{ \beta_1 } d^2$	$\delta = -0.02$

### 10.1.5 Missing Data Imputation

Missing data will be imputed using the following methods for the efficacy analyses:

- Non-Responder Imputation (NRI): the NRI analysis will categorize any subject who does not have evaluation during a specific visit window as a non-responder for that visit. The exception is when the subject is a responder both before and after a specific visit window, in which case the subject will be categorized as a responder for the visit. Only observations within the same analysis period will be used. The NRI will be the primary approach in the analyses of categorical variables.

- Last Observation Carried Forward (LOCF): The LOCF analyses will carry forward the most recent previous non-missing value (last completed non-missing value, for composite endpoint) to impute missing data at later visits in the same period. Baseline efficacy evaluations will not be carried forward. LOCF will be the primary approach in the analyses of continuous variables, and the secondary approach in the analysis of categorical variables.
- As-Observed Cases (OC): The as-observed analysis will not impute values for missing evaluations, and thus a subject who does not have an evaluation on a scheduled visit will be excluded from the as-observed analysis for that visit. As-observed analysis will be the secondary approach in the analysis of continuous variables.
- Multiple Imputation (MI): The MI approach will be used for sensitivity analyses on the Week 16 endpoints of EASI percent change from Baseline, EASI 75, and the Investigator Global Assessment (IGA) response of 0 (clear) or 1 (almost clear). If MI is not applicable due to the nature of the data (e.g., MCMC algorithm does not converge), logistic regression or mixed effect model repeat measurement (MMRM) methods will be applied as the sensitivity approach, whichever applicable.

The Multiple Imputation analysis will be carried out in three steps.

- Imputation of missing data. The imputation will be generated for each efficacy endpoint measurement. The variables to be included in the imputation model are: Baseline EASI (or IGA), treatment group, and measurements at each visit up to the end of the analysis period. For each endpoint, 20 'complete' datasets will be generated using SAS PROC MI. The imputed post-baseline measurements will be rounded to the same precision as the observed data before the determination of responder status (e.g., EASI 75 and EASI percentage change from Baseline).
  - Analysis of imputed data sets. Using the corresponding statistical methods for the categorical and continuous endpoints, the imputed endpoints from Step 2 will be analyzed using each of the 20 datasets.
-

- Synthesis of imputation and analysis results. SAS PROC MIANALYZE will be used to generate the final inferences of the risk difference between treatment groups.

Of note, subjects who take rescue upadacitinib 30 mg or take rescue topical treatment in Period 2 will have their efficacy assessments taken from the date after the first dose of rescue excluded from the analyses, as the result, the subjects will be considered as non-responders in the NRI approach, and have their last observations on or prior to the date of rescue carried forward, and be removed from the OC approach.

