## 5.2 Variables Used for Stratification of Randomization

For Period 1, the randomization will be stratified by geographic region (US/PR/Canada, EU/AUS, and Japan); for Period 2, the re-randomization will be stratified by geographic region and EASI 75 response at Week 16.

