### **10.3 Primary Efficacy Analysis**

The primary efficacy variable is the percent (%) change from Baseline in EASI score at Week 16. The analysis of the primary efficacy variable will be carried out in ITT\_1 with the LOCF missing data imputation. The dose-response relationship will be evaluated by MCP-Mod method.

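### The multiple-imputation model omits geographic region, although the ANCOVA and CMH analyses of the imputed data adjust for it; adding it is nearly free, and the likely bias is small

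*SAP*

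**What the plan says.** Three parts of the SAP bear on this point.

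- **Imputation model.** SAP 10.1.5 states "The variables to be included in the imputation model are: Baseline EASI (or IGA), treatment group, and measurements at each visit", taken to the end of the analysis period. Region is not listed, no other section adds it, and SAP 12.1 does not mention it. The role of the method is also stated: "The MI approach will be used for sensitivity analyses on the Week 16 endpoints of EASI percent change from Baseline", together with EASI 75 and IGA 0/1.
- **Analysis of the imputed data.** The second step of the same section reads "Using the corresponding statistical methods for the categorical and continuous endpoints". For a continuous endpoint, SAP 10.1.2 specifies an ANCOVA "model with treatment group and stratification factors as fixed effects, and the corresponding baseline value as covariates". For a binary endpoint, SAP 10.1.1 specifies a CMH test and Mantel-Haenszel risk differences, both adjusted for the stratification factors.
- **Stratification.** SAP 5.2: "For Period 1, the randomization will be stratified by geographic region", with three levels (US/PR/Canada, EU/AUS, Japan). It is the only Period 1 factor.

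The primary analysis is separate. SAP 10.3 analyses percent change in EASI "with the LOCF missing data imputation" and adds "The dose-response relationship will be evaluated by MCP-Mod method". No region term is stated for it.

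**The concern.** An imputation model should contain at least the covariates of the analysis applied afterwards. Here, missing Week 16 values are drawn as if region told us nothing beyond baseline, arm and earlier visits. The ANCOVA then estimates region effects from data in which the imputed part carries a weakened regional signal.

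Stratified randomisation balances who enters each arm within region. It does not balance who is missing at Week 16. If a poorly responding region loses more subjects on placebo than on active drug, the imputed placebo mean is pulled towards the regions that stayed, and the treatment difference moves.

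What is at stake is the credibility of the one method that the plan names as a sensitivity analysis for the primary endpoint, EASI 75 and IGA 0/1.

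**Working it through.** **Inputs from the documents** (SAP 4.2 and 4.3): 40 per group; assumed improvements of 35, 45, 60 and 70%; SD 40; two-sided 5% for pairwise tests; Japan capped at 10%, about 4 per group.

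**The plan's own figures.** The SE of a pairwise difference is 40 × √(2/40) = 8.94 points.
- 30 mg versus placebo: 35/8.94 − 1.96 = 1.95, power 97.5% (97.2% by noncentral t), against 97% stated.
- 15 mg versus placebo: 25/8.94 − 1.96 = 0.84, power 79.8% (78.8% by t), against 78% stated.
- MCP-Mod power by simulation: 99.3% with the five protocol models, against 99% stated.

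The stated figures are reproduced within 2 points, so 8.94 is a fair yardstick.

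**Assumptions, because the documents give none.** Regions 45/45/10%. Response differs by 10 or 20 points between the two large regions, with the third midway. Dropout is 25% versus 5%, or 40% versus 10%, in the two large regions, with the third midway. Adjacent-visit correlation is 0.5 or 0.8.

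**Hand calculation, ignoring earlier visits.** Omitting region gives each dropout the mean of the completers in the same arm. The bias in an arm mean is then

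dropout fraction × (mean region effect in completers − mean region effect in dropouts).

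Take region effects +10, −10, 0 and dropout 40%, 10%, 25%.
- Dropouts: 0.45×0.40 = 0.180, 0.45×0.10 = 0.045, 0.10×0.25 = 0.025, total 0.25. Mean effect (1.80 − 0.45)/0.25 = +5.4.
- Completers: 0.270, 0.405, 0.075, total 0.75. Mean effect (2.70 − 4.05)/0.75 = −1.8.
- Bias in the arm mean: 0.25 × (−1.8 − 5.4) = −1.8 points.

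Bias in the difference, active minus placebo:
- same pattern in both arms: −1.8 − (−1.8) = 0;
- active dropout flat at 10%: 0 − (−1.8) = +1.8;
- pattern reversed on active: +1.8 − (−1.8) = +3.6.

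**Simulation with earlier visits in the imputation model.** Placebo versus 30 mg; five visits; monotone dropout after at least one post-baseline visit; sequential normal regression imputation; then a model with treatment and region; 3 × 400,000 subjects per scenario. Baseline EASI was not simulated. Bias in points with region omitted, at correlation 0.5 / 0.8:

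| Regional dropout pattern | 10-point gap, 5 v 25% | 10-point gap, 10 v 40% | 20-point gap, 5 v 25% | 20-point gap, 10 v 40% |
|---|---|---|---|---|
| Same in both arms | −0.05 / 0.00 | 0.00 / −0.08 | 0.04 / 0.00 | 0.04 / −0.07 |
| Varies on placebo only | 0.44 / 0.26 | 0.67 / 0.44 | 0.88 / 0.51 | 1.36 / 0.96 |
| Reversed between arms | 0.84 / 0.60 | 1.44 / 0.98 | 1.66 / 1.15 | 2.69 / 1.90 |

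With region included, the bias is at most 0.06 points in every cell, which is simulation error. The last column lies below the hand values of 1.8 and 3.6 because the observed visits carry part of the regional difference.

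In SE units: 0.08/8.94 = 0.01 at most for the same pattern; 0.26/8.94 = 0.03 to 1.36/8.94 = 0.15 for placebo only; 0.60/8.94 = 0.07 to 2.69/8.94 = 0.30 for the reversed pattern.

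**Trial-sized check.** 700 paired trials per scenario, 40 per arm, regions 18/18/4, 20 imputations. Missingness was 35/20/15/12% by arm, multiplied by 1.6 in one region and 0.5 in the others (assumed). Omitting region shifted the 30 mg difference by +0.45 points with a 10-point region effect, and by +0.80 or −0.92 with 20 points depending on sign, each ± about 0.14. With missingness equal across regions the shift was −0.2 to 0.0.

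**The case against.** The case for leaving the plan alone has real force.

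- **Bias whenever regions differ.** A reader might infer that the sensitivity analysis is biased as soon as dropout and response both vary by region. That is not so. Randomisation is stratified by region and treatment is in the imputation model, so with the same regional dropout pattern in both arms the arm means shift together and the difference does not move.
- **The only check on LOCF.** A reader might also take multiple imputation to be the sole check. SAP 10.1.5 plans as-observed analysis as the secondary approach for continuous variables and LOCF as the secondary approach for categorical ones, where non-responder imputation is primary. Logistic regression or MMRM stands in if imputation proves inapplicable.
- **The primary result.** It does not depend on this model. SAP 10.1.4 and 10.3 apply MCP-Mod to LOCF data. That the imputed EASI data go to ANCOVA is a reading of the wording in SAP 10.1.5. It is the natural reading, since MCP-Mod is tied to LOCF, but it is not spelled out.
- **Size.** Every driver of the bias is assumed, and some values are harsh: 35% × 1.6 is 56% placebo missingness in one region. Protocol 5.1 and 5.4.1 ask subjects who stop study drug to keep attending visits, which works against missing data.

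All four stand as limits on the point. None supplies a reason to exclude region. Arm-specific dropout is plausible: the mandatory Period 1 stop for EASI worsening is likelier to be met on placebo under the plan's own assumed means, although stopping drug need not mean missing data.

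**Conclusion.** The point holds as a minor, nearly free improvement. The imputation model in SAP 10.1.5 omits the randomisation stratum that the following ANCOVA and CMH analyses adjust for.

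Bias in the imputed treatment difference arises only if regional dropout patterns differ between arms, given the observed visits, or possibly if the treatment effect itself differs by region, which was not simulated. In the assumed scenarios it is 0.3 to 1.4 points when only placebo dropout varies by region. It reaches 2.7 points in the extreme reversed pattern, about 8% of the assumed 35-point effect (2.69/35).

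These sizes rest on assumed dropout, region effects and visit correlations, and on the 30 mg versus placebo comparison of percent change in EASI. EASI 75 and IGA 0/1 were not simulated. The documents do not support the conclusion that the primary result is at risk or that any conclusion would change.

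**What to change.** In SAP 10.1.5, add geographic region (US/PR/Canada, EU/AUS, Japan) to the imputation model as indicator variables beside the treatment indicators, for all three Week 16 endpoints. Use the region coding of the analysis model, which under SAP 5.1 is the actual stratum. Make the change before the Period 1 unblinding.

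The cost is two more indicators in the imputation call. Sample size, alpha and stated power do not change. The one small drawback is the sparse Japan level: 10% of 160 is about 16 subjects, or 4 per group. The SAP already foresees that the MCMC algorithm may fail to converge, so region should enter as a main effect only, without a region-by-treatment term.
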